Official title: Mobile mindfulness to improve psychological distress after critical illness

Document date: May 9, 2016

NCT number: NCT02701361

Statistical analysis

Contextual framing of feasibility success was performed by comparing observed vs. *a priori*-stated benchmark frequencies for key study milestones such as rates of attrition, adherence to telephone sessions, and interview completion. Similarly, comparison of observed to benchmark means was performed for acceptability (CSQ) and usability (SUS), as well as examination of participant feedback from post-intervention semi-structured interviews.

For all distress outcomes, we estimated mean changes and corresponding CIs from baseline to each follow up for each treatment group using general linear models and SAS PROC MIXED (SAS Institute, Cary NC). Models were fit with a compound symmetry correlation between patients' repeated measures.

Methods and SAS Code

In the following code for the psychological distress outcome models, the analysis dataset

– intdata – is stacked and sorted, in ascending order by patient (variable name=record_ID) and time point (variable name=interview), such that there is one record per patient per time point.

In the model, FOLLOW1 and FOLLOW2 are indicator variables for the two follow-up interviews, respectively; arm_mm is the indicator variable for the mobile mindfulness group, and tm_arm is the indicator variable for the telephone mindfulness group, with education group as the referent category.

SAS Code for the following outcomes (presented in [Table 2](#) and [eTable 4](#)):

```
proc mixed data = intdata;
class record_ID int;
model outcome= Follow1 Follow2 arm_mm arm_tm arm_mm*Follow1 arm_mm*Follow2
arm_tm*FOLLOW1 arm_tm*FOLLOW2 /ddfm=kr solution residual cl;
repeated interview/subject = record_ID type = cs rcorr;
estimate 'ED Intercept' intercept 1/cl;
estimate 'ED at Follow1' intercept 1 follow1 1/cl;
estimate 'ED at Follow2' intercept 1 follow2 1/cl;
estimate 'MM baseline' intercept 1 arm_mm 1 /cl;

estimate 'MM at follow1' intercept 1 arm_mm 1 Follow1 1 arm_mm*Follow1 1/cl;

estimate 'MM at follow2' intercept 1 arm_mm 1 Follow2 1 arm_mm*Follow2 1/cl;

estimate 'TM baseline' intercept 1 arm_tm 1 /cl;
```

estimate 'TM at follow1' intercept 1 Follow1 1 arm_tm*Follow1 1/cl;

estimate 'TM at follow2' intercept 1 Follow2 1 arm_tm*Follow2 1/cl;

estimate 'ED at Follow1 differential from baseline' Follow1 1/cl;

estimate 'ED at Follow2 differential from baseline' Follow2 1/cl;

estimate 'MM at Follow1 differential from baseline' Follow1 1 arm_mm*Follow1 1/cl; estimate
'MM at Follow2 differential from baseline' Follow2 1 arm_mm*Follow2 1/cl;

estimate 'TM at Follow1 differential from baseline' Follow1 1 arm_tm*Follow1 1/cl;

estimate 'TM at Follow2 differential from baseline' Follow2 1 arm_tm*Follow2 1/cl;

estimate 'MM vs ED change from baseline to follow1' arm_mm*Follow1 1/cl; estimate 'MM vs
ED change from baseline to follow2' arm_mm*Follow2 1/cl;

estimate 'TM vs ED change from baseline to follow1' arm_tm*Follow1 1/cl;

estimate 'TM vs ED change from baseline to follow2' arm_tm*Follow2 1/cl;

contrast "Overall treatment test for FOLLOW1" arm_mm*FOLLOW1 1 ,

contrast "Overall treatment test for FOLLOW2" arm_mm*FOLLOW2 1 ,

run;

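### Does the mismatch between `int` in the CLASS statement and `interview` in the REPEATED statement undermine the distress-outcome model?

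*SAP*

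**What the plan says.** In the Statistical analysis section, the SAP says the distress outcomes are analysed with general linear models in PROC MIXED and fixes the within-patient structure: "Models were fit with a compound symmetry correlation".

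Methods and SAS Code then describes the dataset. It is sorted in "ascending order by patient (variable name=record_ID") and then by "time point (variable name=interview"), "such that there is one record per patient per time point". The two follow-up visits have their own indicator variables, and these carry visit in the MODEL statement.

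The program opens with "proc mixed data = intdata", declares "class record_ID int", and specifies the covariance as "repeated interview/subject = record_ID type = cs rcorr". So `interview` is the repeated effect but is not in CLASS, while `int` is in CLASS but is not used as a variable anywhere else.

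**The concern.** PROC MIXED requires a repeated effect to be built from CLASS variables. The printed call breaks that rule, so it returns no estimates. Because this call is the only model set out for the distress outcomes, a reader who takes the listing at face value cannot reproduce the analysis.

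There is also a less obvious worry. One quick way to make the step run is to delete the effect from the REPEATED statement. SAS then assigns occasions by the order of records within a patient. If a patient has baseline and follow-up 2 but no row for follow-up 1, follow-up 2 is taken as the second occasion. Under a covariance structure that differs by occasion, that patient's residuals would be placed at the wrong time point. The SAP lists attrition and interview completion among its feasibility milestones, so gaps of this kind are conceivable.

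**Working it through.** The plan gives no figure to reproduce here. The check compares variable names across statements and then asks whether the repair chosen can alter a result.

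**Names, side by side**

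| Role | Prose | CLASS | REPEATED | MODEL |
|---|---|---|---|---|
| Patient | `record_ID` | `record_ID` | `record_ID` (subject) | not used |
| Time point | `interview` | `int` | `interview` (effect) | not used; visit enters through the two follow-up indicators |

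**Does the printed step run?**

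1. If the dataset has no variable `int`, as the document's definitions imply, the CLASS statement fails because the variable is not found.
2. If the dataset does hold an undocumented `int`, the REPEATED statement fails because `interview` is not a CLASS variable.

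It stops in either case. It does not run and return something wrong.

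**Does the choice of repair matter?** Three repairs suggest themselves: put `interview` in CLASS; use `int` in both places, if such a variable exists and marks the visits; or drop the repeated effect and rely on record order.

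- *Mean model.* The fixed effects use the follow-up indicators, the arm indicators and their products. None of these depends on CLASS or on the repeated effect. A follow-up 2 record keeps its follow-up 2 mean under all three repairs.
- *Covariance.* Under compound symmetry, a patient with n observed visits has covariance matrix V = s²I + cJ, where I is the n × n identity matrix, J is the n × n matrix of ones, and s² and c are the two covariance parameters. Every diagonal element is s² + c and every off-diagonal element is c.
  - Reordering visits with a permutation matrix P gives PVP′ = s²PIP′ + cPJP′ = s²I + cJ = V.
  - For a patient with all three visits (n = 3), relabelling them therefore leaves V unchanged.
  - For a patient with two visits (n = 2), the diagonal is s² + c and the covariance is c, whether the pair is baseline and follow-up 1 or baseline and follow-up 2. Treating follow-up 2 as the second occasion changes nothing.
- *Inference.* The likelihood, the fixed-effect estimates and the Kenward–Roger standard errors and degrees of freedom depend on the repeated effect only through V and its derivatives with respect to s² and c. Those derivatives are I and J, which are also unchanged by reordering.

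All three repairs therefore give the same estimates and the same confidence intervals.

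**What misalignment would need.** Three things must happen together: the analyst drops the repeated effect; the structure is changed to one that depends on occasion, such as unstructured, which the SAP does not use; and rows for missed visits are absent. On the third, the stated layout is one record for each patient at each time point. Read literally, a missed interview still has a row with a missing outcome, and record order then preserves its position.

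**The case for a change.** The best case for acting is that a plan which fixes its analysis by printing code should print code that runs. The line is intact, ends in a semicolon and shows no sign of redaction, so the mismatch cannot be put down to text lost from the PDF. More than one repair is possible, the correction costs one word, and the same edit could settle a similar slip: the telephone indicator is `tm_arm` in the prose and `arm_tm` in the code.

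The factual part stands. The mismatch is real, and the step fails as printed whatever the dataset contains.

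The consequences do not follow:

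- Saying the analysis cannot be reproduced goes too far. The prose supplies the patient variable, the time variable, the referent group and the covariance structure, and the MODEL statement is complete. An analyst who meets the error finds the right name in the paragraph above.
- The SAP does not say that it expects attrition. It compares attrition and interview completion with benchmarks, gives no rate in this document, and does not mention intermittent gaps.
- Harm under an unstructured covariance belongs to a different plan. If the structure were ever changed, the time variable would have to be named correctly then.

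One caution is fair: correcting this line would not make the whole listing right. The ESTIMATE statements for the telephone arm's means at the two follow-ups omit the arm main effect that the mobile arm's statements include. Unlike the present slip, that would give wrong numbers without an error. It is a separate matter, and nothing said here excuses it.

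**Conclusion.** This is a clerical slip in a code listing. `int` is most likely an abbreviation or transcription error for `interview`. The document describes the fitting in the past tense and points to results tables, which suggests, without proving it, that a working program lay behind the listing.

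The effect on any estimate, confidence interval or conclusion is nil. Anyone running the program is stopped at once and has the correct name to hand, and the consistent repairs agree exactly. The `tm_arm`/`arm_tm` mismatch is equally easy to resolve from the context. No change to the plan is needed on this point.

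The conclusion rests on two things: the compound symmetry structure stays as specified, and visit stays in the mean model through the follow-up indicators, as printed. It does not depend on whether the dataset happens to contain a variable called `int`, nor on how many patients missed an interview.

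### The MM vs ED and TM vs ED distress contrasts fix the baseline slope at 1; under the SAP's equal-variance model, baseline adjustment would make them more precise at little cost.

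*SAP*

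**What the plan says.** For the distress outcomes, the SAP's Statistical analysis section says "we estimated mean changes and corresponding CIs from baseline to each follow up for each treatment group". It sets the covariance as follows: "Models were fit with a compound symmetry correlation between" a patient's repeated measures. It also lists "rates of attrition, adherence to telephone sessions, and interview completion" among the feasibility milestones, so some loss to follow-up is expected.

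Under Methods and SAS Code, the data are stacked "such that there is one record per patient per time point", which makes the baseline score a row of the outcome. The MODEL statement begins "model outcome= Follow1 Follow2 arm_mm arm_tm arm_mm*Follow1 arm_mm*Follow2" and continues with the matching telephone-arm interactions. The terms arm_mm and arm_tm leave the baseline mean free in each arm, and there is no baseline covariate.

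The between-arm comparisons appear only in the code. They are the interaction coefficients, each with a CI: "estimate 'TM vs ED change from baseline to follow1' arm_tm*Follow1 1/cl" and "estimate 'TM vs ED change from baseline to follow2' arm_tm*Follow2 1/cl", plus the same pair for mobile mindfulness (MM). Two overall tests are also requested, the first titled "Overall treatment test for FOLLOW1". Their code breaks off after the MM term in the text at hand, so only their titles are used here.

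**The concern.** A difference in change subtracts the whole baseline difference between two arms. Under compound symmetry, the regression of follow-up on baseline has slope rho, not 1. The SAP's own covariance model therefore implies that its contrasts subtract too much.

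This has two consequences. Each between-arm CI is wider than the same data allow. And an arm that starts high by chance appears to improve more than it did, which matters most when arms are small. Only the between-arm results are touched. The within-arm changes and the feasibility, acceptability and usability benchmarks are not.

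**Working it through.** **Inputs.** From the SAP: the mean model, the stacked layout, type = cs, and the four interaction contrasts. The SAP gives no rho, SDs, arm sizes or dropout, so there is no stated figure to reproduce. Assumed: rho 0.3, 0.5, 0.7; n = 15 or 30 per arm; either complete data or 20% missing at Follow1 and 40% at Follow2; equal expected baseline means, as under randomisation.

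**1. Weight on baseline.** Generalised least squares on the three-arm, three-visit design puts a weight of exactly 1 on the baseline difference between arms. This holds for every rho from 0 to 0.9, with complete data and with 20% of follow-up missing.

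**2. Large-sample variance, complete data.** With variance sigma² at each visit:

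- Planned contrast: 2(1 − rho) × 2sigma²/n
- Baseline-adjusted contrast: (1 − rho²) × 2sigma²/n
- Difference: (1 − rho)² × 2sigma²/n
- Ratio, adjusted to planned: (1 + rho)/2

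At rho 0.5 and n = 30, the SEs are √(1.00 × 2/30) = 0.258 SD planned and √(0.75 × 2/30) = 0.224 SD adjusted.

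**3. Dropout.** The difference stays at (1 − rho)² = 0.49, 0.25, 0.09 in units of 2sigma²/n. At Follow1 with rho 0.5, the adjusted term is 0.75/0.8 = 0.9375, the planned term is 0.9375 + 0.25 = 1.1875, and the ratio is 0.79. At n = 30 the SEs are 0.281 planned and 0.250 adjusted (Follow1), and 0.313 and 0.285 (Follow2).

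**4. Summary, equal variances (adjusted/planned).**

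| Quantity | rho 0.3 | rho 0.5 | rho 0.7 |
|---|---|---|---|
| Variance, complete data, large sample | 0.65 | 0.75 | 0.85 |
| Variance, Follow1, 20% missing, large sample | 0.70 | 0.79 | 0.88 |
| Variance, Follow2, 40% missing, large sample | 0.75 | 0.83 | 0.90 |
| CI width, complete data, n = 30, simulated | 0.82 | 0.88 | 0.93 |
| CI width, complete data, n = 15, simulated | 0.83 | 0.89 | 0.95 |
| CI width, Follow1 with dropout, n = 15, simulated | 0.87 | 0.92 | 0.97 |
| CI width, Follow2 with dropout, n = 15, simulated | 0.91 | 0.96 | 0.99 |

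The complete-data simulation used 40,000 runs, with 2(3n − 3) df for the planned model and 3n − 4 for the adjusted one (84 and 41 at n = 15). Coverage was 0.949 to 0.952 for both. The dropout simulation used 6,000 runs with REML fits and df approximated from observed counts, not Kenward-Roger. Coverage was 0.945 to 0.955 (planned) and 0.944 to 0.955 (adjusted).

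**5. Chance imbalance.** The baseline difference between two arms has SD √(2/n) in units of sigma. The chance that it is 0.3 SD or more in either direction is 41% at n = 15 and 25% at n = 30. Given a 0.3 SD imbalance, the planned contrast over-corrects by (1 − rho) × 0.3 = 0.21, 0.15, 0.09 SD. In simulation at n = 30, the planned contrast regressed on the imbalance had slopes −0.70, −0.50, −0.30; the adjusted one had 0.00 each time.

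**6. Unequal variances.** Let k be the follow-up/baseline SD ratio. The true slope is rho × k, and the complete-data variance ratio is k²(1 − rho²)/(k² + 1 − 2 rho k). At k = 1.3:

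| rho | 0.3 | 0.5 | 0.7 | 0.77 | 0.8 |
|---|---|---|---|---|---|
| True slope | 0.39 | 0.65 | 0.91 | 1.00 | 1.04 |
| Variance ratio | 0.81 | 0.91 | 0.99 | 1.00 | 1.00 |
| Over-correction at 0.3 SD imbalance (SD) | 0.18 | 0.11 | 0.03 | 0 | −0.01 |

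The last entry is an under-correction. Over-correction holds only while rho × k is below 1.

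**The case against.** The strongest reply is that nothing here is wrong. A longitudinal model with free arm means is standard, it serves the aim that the prose states, and no decision rests on the between-arm contrasts. All of that stands, and it is why this is a suggestion and not an error.

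The gain also rests on facts that the SAP does not give. Without randomisation, or with baseline taken after allocation, the two analyses target different quantities. With n = 15 and dropout, the CIs narrow by only 4% to 8% at rho 0.5 and 1% to 3% at rho 0.7. Differences that small are sensitive to the df approximation, since the SAP asks for Kenward-Roger. These limits stand too, so the recommendation is conditional and the size is a range.

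A smaller edit exists: drop arm_mm and arm_tm so that the arms share one baseline mean. In a 1,000-run check (n = 15, same dropout), its SE ratios to the planned contrast at Follow1 and Follow2 were 0.83 and 0.87 at rho 0.3, and 0.89 and 0.91 at rho 0.5. That looks slightly better than the CI width ratios of 0.87 and 0.91, and 0.92 and 0.96, for the follow-up model, although SE ratios leave out any change in df. But the edit relies on compound symmetry being right, because that fixes the slope at the common correlation. A baseline slope estimated at each visit does not need that assumption.

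Finally, the SAP is written in the past tense and points to result tables. If results were known, adjusted contrasts can only be labelled post hoc.

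**Conclusion.** The point holds as a low-cost improvement, worth considering, with medium confidence. The planned contrasts are valid. If arms were randomised after baseline, they are also unbiased on average, but under the SAP's equal-variance model they are less precise than they need be. At rho 0.5 with complete data, the large-sample CI is about 15% wider than necessary (1/0.866 = 1.155). For rho 0.3 to 0.7 with 15 per arm, adjustment narrows the CI by 17% to 5% with complete data, 13% to 3% at Follow1 with dropout, and 9% to 1% at Follow2. If follow-up scores are more variable than baseline, the gain is smaller and is nil where rho times the SD ratio equals 1. All sizes rest on assumed values.

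**What to change.** Keep the SAP's model and ESTIMATE statements for the within-arm changes and their CIs. If arms were randomised and baseline was measured before allocation, take the four between-arm contrasts and the two overall tests from a second model:

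- outcome: the two follow-up scores;
- fixed terms: visit, arm-by-visit, and baseline score with a slope that may differ by visit;
- covariance: unstructured for the two follow-ups.

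If either condition fails, keep the planned contrasts. If results were already known, label the adjusted contrasts post hoc and show them beside the planned ones.

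The cost is one extra model per outcome and a few parameters. Where the true slope is 1 (SD ratio 1.3, rho 0.77, n = 15), adjustment loses a little. Its variance is 2% larger with complete data (CI under 1% wider). With 20%/40% dropout it is 2% larger at Follow1 and 4% at Follow2 (CIs 3% and 6% wider). The between-arm estimates will no longer equal the difference of the reported within-arm changes (a gap of 0.15 SD for a 0.3 SD imbalance at rho 0.5), so the table needs a footnote. Patients with no baseline score or no follow-up drop out of the second model but stay in the within-arm one.

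### The two ESTIMATE statements for the telephone mindfulness follow-up means omit the arm main effect, so they return education-arm baseline plus telephone-arm change

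*SAP*

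**What the plan says.** The SAP's Statistical analysis section names its target for the distress outcomes: "we estimated mean changes and corresponding CIs from baseline to each follow up for each treatment group". Under Methods and SAS Code it lists one PROC MIXED program, headed as serving the outcomes in Table 2 and eTable 4. Education (ED) is the referent. The MODEL statement contains two follow-up indicators, main effects for mobile mindfulness (MM) and telephone mindfulness (TM), and all four arm-by-follow-up interactions.

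The two TM follow-up means are coded as:

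- "estimate 'TM at follow1' intercept 1 Follow1 1 arm_tm*Follow1 1/cl"
- "estimate 'TM at follow2' intercept 1 Follow2 1 arm_tm*Follow2 1/cl"

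The TM baseline mean and the corresponding MM follow-up mean are coded as:

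- "estimate 'TM baseline' intercept 1 arm_tm 1 /cl"
- "estimate 'MM at follow1' intercept 1 arm_mm 1 Follow1 1 arm_mm*Follow1 1/cl"

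The TM change and the TM vs ED difference in change at the first follow-up are:

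- "estimate 'TM at Follow1 differential from baseline' Follow1 1 arm_tm*Follow1 1/cl"
- "estimate 'TM vs ED change from baseline to follow1' arm_tm*Follow1 1/cl"

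**The concern.** The TM baseline line and both MM follow-up lines carry their arm main effect; the two TM follow-up lines do not. A model term left out of an ESTIMATE statement for a 0/1 covariate gets coefficient zero, so these lines estimate something other than their label.

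At stake are the TM follow-up level means and their CIs, for every outcome run through the code. Within one output, TM baseline plus TM change would not equal the TM follow-up mean, and TM levels would be defined differently from MM and ED levels. A reader comparing levels across arms would be misled, and nothing in the output would flag it.

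**Working it through.** **Inputs.** The model terms, the 0/1 coding and the ED referent come from Methods and SAS Code. The SAP gives no arm sizes, within-patient correlation ρ, outcome SD, dropout or baseline difference, so every value used for these below is an assumption. It states no figure on this point to reproduce.

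**Step 1: labelled target against printed code.** Let β0 be the intercept, βFk the effect of follow-up k (k = 1, 2), βMM and βTM the arm main effects, and βMM,Fk and βTM,Fk the interactions.

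| Quantity | Target | Printed |
|---|---|---|
| ED baseline | β0 | same |
| TM baseline | β0 + βTM | same |
| MM at follow-up k | β0 + βMM + βFk + βMM,Fk | same |
| **TM at follow-up k** | **β0 + βTM + βFk + βTM,Fk** | **β0 + βFk + βTM,Fk** |
| TM change to k | βFk + βTM,Fk | same |
| TM vs ED change to k | βTM,Fk | same |

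The printed TM follow-up expression is β0 + (βFk + βTM,Fk), which is ED baseline plus TM change. Printed minus target is −βTM at both follow-ups.

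**Step 2: extent.** Of the 19 ESTIMATE statements, 17 match their labels: 7 level means, 6 changes from baseline and 4 differences in change vs ED. The other 2 are these.

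**Step 3: numerical check.** The model was fitted by generalised least squares with compound symmetry to one simulated data set (assumed 25 per arm, SD 5, ρ = 0.5, about 15% missing at each follow-up, true baseline gap 3 units). At the first follow-up:

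- printed contrast: 4.436, which equals ED baseline 8.034 + TM change (−3.598)
- correct contrast: 9.903, which equals TM baseline (8.034 + 5.467 = 13.501) + TM change (−3.598)
- difference: 4.436 − 9.903 = −5.467, that is, −βTM as fitted

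This confirms the identity. It says nothing about the size of the error in the trial.

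**Step 4: size of the shift if the baseline gap is chance alone.** With n per arm and outcome SD 1, SD(βTM) = √(2/n), and the expected absolute value is √(2/n) × √(2/π). The correct 95% half-width with complete data is 1.96/√n.

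| n per arm | SD of gap | Expected absolute gap | Correct half-width | Ratio |
|---|---|---|---|---|
| 20 | 0.316 | 0.252 | 0.438 | 0.576 |
| 30 | 0.258 | 0.206 | 0.358 | 0.576 |
| 40 | 0.224 | 0.178 | 0.310 | 0.576 |

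The ratio is √2 × √(2/π) / 1.96 and does not depend on n.

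**Step 5: standard error, variance components taken as known.** With complete data, the ED baseline mean and the TM change come from different patients, so

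- Var(printed) = σ²/n_ED + 2σ²(1 − ρ)/n_TM
- Var(correct) = σ²/n_TM
- SE ratio = √(n_TM/n_ED + 2 − 2ρ)

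| Arms (complete data) | ρ = 0.3 | ρ = 0.5 | ρ = 0.7 |
|---|---|---|---|
| equal | √2.4 = 1.549 | √2.0 = 1.414 | √1.6 = 1.265 |
| TM 30, ED 20 | 1.703 | 1.581 | 1.449 |
| TM 20, ED 30 | 1.438 | 1.291 | 1.125 |

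Dropout narrows the ratio only a little. Take 30 per arm, with 15% of the original number lost by the first follow-up and 30% by the second. At ρ = 0.5 and the first follow-up (25.5 patients remaining):

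- Var(correct)/σ² = 0.75/25.5 + 0.25/30 = 0.03775
- Var(printed)/σ² = 1/30 + 0.75/25.5 + 0.25/30 = 0.07108
- SE ratio = √(0.07108/0.03775) = 1.372

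Across ρ = 0.3, 0.5 and 0.7 the ratios are 1.485, 1.372 and 1.245 at the first follow-up, and 1.420, 1.330 and 1.225 at the second.

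The printed interval is not wider in every case. It is wider when ρ < (1 + n_TM/n_ED)/2, which always holds for equal arms with ρ < 1. With TM 20, ED 30 and ρ = 0.9 the ratio is √(0.667 + 0.2) = 0.93.

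**The case against.** The algebra is not in dispute; the weight is.

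- **The named target is intact.** The SAP promises mean changes, and all six change estimates and all four differences vs ED are right. This stands: the fault is confined to two level means in one arm, and no named comparison or feasibility benchmark rests on them.
- **The listing may not be what was run.** CLASS names `int`, while the REPEATED line is "repeated interview/subject = record_ID type = cs rcorr", so the listing would probably stop before giving any estimate. The prose calls the TM indicator `tm_arm`, but the code uses `arm_tm`. The text is in the past tense and cites existing tables. Both CONTRAST statements end in a comma, although a second row may have been lost in PDF conversion. This also stands: an error in the listing is established, an error in a reported result is not. But a CLASS/REPEATED mismatch would be expected to fail visibly and be repaired, whereas the missing main effect gives plausible numbers under the wrong label.
- **PDF loss could explain the omission too.** This is unlikely. The term is missing mid-line from two otherwise complete statements and present in both MM counterparts.
- **The magnitudes rest on assumptions.** True. All that follows from the document is an error of −βTM, size and sign unknown.
- **There may be no bias.** If the arms' population baseline means are equal, as randomisation (not mentioned in this document) would imply, the printed contrast has no systematic bias for the TM mean. It still differs from the fitted TM mean in any given data set, usually with a wider interval.

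**Conclusion.** The concern holds. As printed, both TM follow-up lines estimate ED baseline plus TM change. They agree with the fitted TM means only if the fitted TM-minus-ED baseline difference is exactly zero.

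For a chance imbalance, the expected absolute shift is about 0.18 to 0.25 outcome SD at an assumed 40 down to 20 per arm. With equal arms and complete data, the standard error is inflated by a factor of 1.26 to 1.55 for assumed ρ of 0.7 down to 0.3.

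The effect stops at the TM follow-up means and their CIs. Whether Table 2 or eTable 4 used these lines cannot be seen from the SAP. The correction is worth making because the coding error is certain, would recur for each outcome, and costs almost nothing to remove.

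**What to change.** Insert `arm_tm 1` after `intercept 1` in the 'TM at follow1' and 'TM at follow2' statements, matching the MM lines. Check the executed program for the same omission. If it is there, regenerate any TM follow-up means and CIs taken from those lines. For each outcome, confirm that TM baseline plus TM change equals the TM follow-up mean.

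At the same time, reconcile the CLASS and REPEATED variable names and the `tm_arm`/`arm_tm` naming, and check the two CONTRAST statements against the source file.

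The cost is one term in each of two lines, a check of the program and, if needed, a re-run of the level estimates. The change and difference-in-change results need no revision, and nothing changes for patients or the protocol.
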